9.2.2.2 Pharmacodynamic variables

Pharmacodynamic assessments of lymphocyte subsets will be performed in order to characterize the PD profile of 2 treatment courses of alemtuzumab in paediatric patients.

9.2.2.2.1 Assessment methods

Lymphocyte phenotyping

To monitor the extent of lymphocyte depletion and repopulation, lymphocyte phenotyping, including a standard, 6-color TBNK (T cells, B cells, and natural killer cells) panel (CD3+, CD4+, CD8+, CD19+, CD16+, CD56+, total lymphocytes, and helper/suppressor ratio [CD4+/CD8+]), will be performed. Lymphocyte phenotyping will be assessed at screening, D-14 to D-7, M1, M4, M8, M12, M13, M15, M18, M21, M24/at EOTP; annually in Safety Monitoring Phase.

9.2.2.3 Quality of life endpoints

Quality of Life (QoL) will be assessed by established generic paediatric QoL measures.

PedsQL questionnaire

The PedsQL™ Measurement Model is a modular approach to measuring health-related quality of life (HRQOL) in healthy children and adolescents and those with acute and chronic

health conditions. The PedsQL Measurement Model integrates seamlessly both generic core scales and disease-specific modules into one measurement system.

The 23-item PedsQL Generic Core Scales ([Appendix F](#)) were designed to measure the core dimensions of health as delineated by the World Health Organization, as well as role (school) functioning.

Paediatric NeuroQoL questionnaire

Paediatric NeuroQoL (Quality of Life in Neurological Disorders) is a measurement system that evaluates and monitors the physical, mental, and social effects experienced by children living with neurological conditions. Physical effects (fatigue and pain) and mental effects (cognitive function, anxiety, and depression) experienced by patients will be assessed ([Appendix G](#)).

PedsQL and paediatric NeuroQoL questionnaire will be assessed at Screening, D-14 to D-7, M4, M8, M12, M18, M24/at EOTP; and annually in Safety Monitoring Phase.

9.3 SAFETY ENDPOINTS

Safety endpoints will be assessed by:

- AE reporting at each visit.
- Physical examination and vital signs: Screening, D-14 to D-7, M0/D1, M4, M8, M12, M15, M18, M21, M24/at EOTP; every 6 months in the safety monitoring phase, and at every relapse visit.
- Additionally, vital signs will be collected hourly during alemtuzumab infusion and post infusion observation period.
- Clinical chemistry laboratories: Screening, D-14 to D-7, M4, M8, M12, M15, M18, M21, M24/at EOTP; quarterly in the safety monitoring phase. In addition, only serum creatinine will be assessed at M0/D1, monthly in alemtuzumab treatment phase (Year 1 and 2); monthly in the safety monitoring phase (inclusive of chemistry panel).
- Hematology: Screening, D-14 to D -7, M0/D1, and monthly in alemtuzumab treatment phase (Year 1 and 2); EOTP, and monthly in the safety monitoring phase.
- Urinalysis: Screening, D-14 to D -7, monthly in alemtuzumab treatment phase (Year 1 and 2); EOTP, and monthly in the safety monitoring phase.
- Thyroid Function tests: Screening, D-14 to D -7, quarterly in alemtuzumab treatment phase (Year 1 and 2); EOTP, and quarterly in the safety monitoring phase.
- Tanner staging: Screening, M12, M24/at EOTP; annually in the safety monitoring phase.
- Pregnancy testing (females only): Screening (blood test), D-14 to D -7 and M12 (urine test).
- Assessment of ADA: M0/D1 (baseline), post dose M1, M3, M12 (prenext dose), M13, M15, M24/at EOTP; and annually in the safety monitoring phase.

9.3.1 Adverse events

Adverse events reported by the patient or observed by the Investigator will be monitored, and include:

- Occurrence, seriousness, grade/intensity, relationship to study drug, resolution, and outcome of serious adverse event (SAE), adverse event of special interest (AESI), and AEs.
- Assessment of IARs: An IAR is defined as any AE occurring during alemtuzumab infusion or within the 24 hour post-infusion period. However, some IARs may occur beyond 24 hours (such as pulmonary alveolar hemorrhage, stroke, cervicocephalic arterial dissection, myocardial ischemia, thrombocytopenia and myocardial infarction). Toxicity grade (severity) of IAR is based on CTCAE. The timing of IAR in relation to alemtuzumab administration and distribution of IARs based on toxicity grade (severity) observed in the study for both study periods will be assessed.

Refer to [Section 10.4.1](#) for details.

9.3.2 Laboratory safety variables

The clinical laboratory data consist of blood analysis (including hematology, clinical chemistry, and urinalysis). Clinical laboratory values will be analyzed after conversion into standard international units. International units will be used in all listings and tables.

All laboratory data listed in this section will be measured at a central laboratory. The laboratory data will be collected at designated visits as shown in study flow chart [Section 1.2](#).

It is preferred that CBCs with platelet count (for monitoring for any cytopenia as well as), serum creatinine, and urinalysis with microscopy be analyzed at the central laboratory, but under special circumstances (eg, if patient is unable to visit the study center weekly or monthly, or results are needed urgently), the assay may be performed at a local laboratory provided that test results are entered into the e-CRF in a timely manner. In addition, at some visits during the safety monitoring phase, there is an option for the nurse to obtain samples for clinical chemistry laboratories, hematology, thyroid function tests, urinalysis and serum creatinine at the patient's home if needed (refer to study flow chart [Section 1.2](#)).

The following laboratory safety variables will be analyzed:

- Hematology and differential panel: red blood cell count, hematocrit, hemoglobin, mean corpuscular hemoglobin, white blood cell count with differential count (neutrophils, eosinophils, basophils, monocytes, and lymphocytes) and platelets.
- Complete Chemistry panel: glucose, serum creatinine, blood urea nitrogen (BUN), sodium, potassium, chloride, bicarbonate, magnesium, calcium, uric acid, aspartate aminotransferase, alanine aminotransferase (ALT), gamma-glutamyl transferase, lactate dehydrogenase, total bilirubin, direct/indirect bilirubin, alkaline phosphatase, inorganic phosphorus, total protein, albumin, globulin, albumin/globulin ratio, triglycerides, total cholesterol and creatinine phosphokinase.

- Urinalysis: pH, ketones, protein, glucose, blood, urobilinogen, bilirubin, microscopic sediment, specific gravity.
- Thyroid function testing: thyroid stimulating hormone and if abnormal T3 and T4.
- Hepatitis B and C serology testing.
- HPV serology testing: Testing will be conducted for human papillomavirus (HPV) infection as and when recommended by local public health authorities. If the testing is positive, the patient may be eligible after the condition has resolved as per the Investigator opinion (eg, follow-up HPV test is negative or cervical abnormality has been effectively treated). An annual follow-up is recommended.
- Tuberculosis test screening. It should be performed as per local health care authority recommendations.

Pregnancy testing: β -Human chorionic gonadotropin.

In accordance with international recommendations (20), sampling blood volume will be minimized to approximately 1% of total blood volume at each visit and approximately 3% of total blood volume over a 4 week period.

Blood sample volume will range from 9 to 57 ml, depending on tests required at study visits (ie, an average blood sample amount of 23 ml per visit). The total amount of blood withdrawn will be approximately 350 ml in Year 1 and 200 ml in Year 2. During the safety monitoring phase, approximately 120 ml will be drawn each year. However, additional blood samples may be collected at the Investigator's discretion for patient safety monitoring.

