	
Safety
 
 • Adverse event (AE) reporting at each visit. • Physical examination and vital signs: Screening, D-14 to D-7, M0/D1, M4, M8, M12, M15, M18, M21, M24/at EOTP; every 6 months safety monitoring phase, and at every relapse visit, if applicable. • Additionally, vital signs will be collected hourly during alemtuzumab infusion and post infusion observation for 2 hours. • Clinical chemistry laboratories: Screening, D-14 to D-7, M4, M8, M12, M15, M18, M21, M24/at EOTP; quarterly in safety monitoring phase. In addition, serum creatinine and alanine aminotransferase will be assessed at M0/D1, monthly in alemtuzumab treatment phase (Year 1 and 2); monthly in the safety monitoring phase (inclusive of chemistry panel). • Hematology: Screening, D-14 to D-7, M0/D1, and monthly in alemtuzumab treatment phase (Year 1 and 2); EOTP and monthly in safety monitoring phase. • Urinalysis: Screening, D-14 to D-7, monthly in alemtuzumab treatment phase (Year 1 and 2); EOTP and monthly in safety monitoring phase. • Thyroid function tests: Screening, D-14 to D-7, quarterly in both Alemtuzumab Treatment Phase (Year 1 and 2); EOTP, and in safety monitoring phase. • Tanner staging: Screening, M12, M24/at EOTP; annually in safety monitoring phase. • Pregnancy testing (females only): Screening (blood test), D-14 to D-7 and M12 (urine test). • Assessment of ADA: M0/D1 (baseline), M1, M3, M12 (prior to second course being administered), M13, M15, and M24/at EOTP; annually in safety monitoring phase. 
Pharmacodynamics
 
 • Lymphocyte phenotyping: Screening, D-14 to D-7, M1, M4, M8, M12, M13, M15, M18, M21, M24/at EOTP; annually in Safety Monitoring Phase. 
Pharmacokinetics

[figure not shown]
	
 For patients receiving alemtuzumab, serum concentrations and PK parameters will be studied. 
Immune Markers (optional)
 
 Immune Markers (optional): M0/D1 (baseline), M4, M12, M18 and M24/at EOTP.

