Interferon-beta (IFNB) and GA have not been formally tested in paediatric MS patients with a relapsing-remitting course during placebo-controlled trials. However, class III and IV evidence of effectiveness resulting from observational open-label studies have prompted their current use and recommendation. Nonetheless, in about 30% of paediatric MS patients, the disease continues to be active despite immunomodulatory treatment, supporting the need to explore other therapeutic options (15). There are few data to support the use of other DMTs in paediatric populations. Considering the high frequency of inadequate response to first-line DMT and the lack of clinical trial data regarding the efficacy of switching to other DMTs, this paediatric population has a high unmet need.

Alemtuzumab dose selection

Alemtuzumab will be administered as a daily intravenous (IV) infusion, similar to adult treatment regimen (course 1 at Month 0, 12 mg on 5 consecutive days, and course 2 at Month 12, 12 mg on 3 consecutive days), giving a cumulative dosage of 60 mg at first course, and 36 mg at second course. The adult dose will be adjusted (reduced) proportionately for paediatric patients <50 kg based on the patient's weight. Calculation of a paediatric patient's dose will be based on patient's last visit weight taken during the physical examination:

- For patients ≥ 50 kg: 12 mg/day.
- For patients <50 kg: 0.24 mg/kg/day (this equates to 12 mg/day for a 50 kg patient).

The 0.24 mg/kg/day dose is based on experience using alemtuzumab in the treatment of children undergoing bone marrow or solid organ transplantation, and is similar to or lower than doses previously used (16). This corresponds to a cumulative dose over 5 days of 1.2 mg/kg at Month 0, with a smaller dose of 0.72 mg/kg at Month 12.

Prophylactic administration of methylprednisolone, antiH1 and antiH2 medications will be a part of the alemtuzumab treatment regimen, to minimize infusion associated reactions.

MRI

The proposed study will have an MRI-based primary endpoint. Recent publications have demonstrated a correlation between the MRI lesions and clinical relapse for IFNB or GA based on meta-analysis of data collected in randomized controlled trials (17), and for alemtuzumab (13). MRI assessments will be available to investigators to assess safety.

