9.2 SECONDARY ENDPOINTS

Secondary endpoints include the efficacy, quality of life and pharmacokinetic/Pharmacodynamic endpoints are listed below, and will be assessed as shown in [Section 9.2.1](#) and [Section 9.2.2](#):

Efficacy:

- The number of patients with new or enlarging T2 lesions during continuation of prior DMT (Period 1) compared to an equal period after the first course of alemtuzumab treatment (Period 2).
- EDSS (descriptive analysis, ie percentages of stable/improved/worsened since the end of Period 1).
- Annualized relapse rate (ARR) at Year 2.
- Cognition test scores: Brief Visuospatial Memory Test – Revised (BVMT-R) and Symbol Digit Modality Test (SDMT); administered at least every 6 months over 2 years.

Quality of life:

- Established generic paediatric QoL measures administered every 6 months over 2 years.

Pharmacokinetics/Pharmacodynamics:

- PK serum concentration and PK parameters (C_{max} , T_{max} , AUC, AUC_{last} , $T_{1/2z}$) calculated where possible.
- PD assessment including lymphocyte subsets.

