 - Perform MRI scan without contrast. It is important to ensure that this MRI assessment is performed 4 months (± 7 days) apart to the MRI assessment on D-7 visit. The MRI assessments will be available to investigators to assess safety.
 - Perform EDSS assessment.
 - Perform SDMT and BVMT-R test.
 - Recording of PedsQL/Ped NeuroQoL.
 - Remind patient to continue on their DMT.
 - Commence AE/SAE reporting.

Note: The above investigations may be performed on separate visits as long as all are completed within the 28 days prior to inclusion (V2, M-4). If any of the examinations/measurements does not fulfill the inclusion/exclusion criteria at the screening visit, they may be repeated before Visit 2.

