10.1.3 Visit 3/Days -14 to -7

Visit 3 assessments can be performed over multiple days as long the time windows below are respected.

The following items will be checked/performed and recorded for all patients:

- Perform MRI scan without contrast. It is important to ensure that this MRI assessment is performed 4 months (± 7 days) from the MRI assessment done at screening.
- Physical examination including vital signs.
- AEs/SAEs (if any) will be monitored.
- Concomitant medication (if any) will be checked and reported.
- Blood and urine sample for laboratory assessments (hematology and chemistry) including thyroid function test; pregnancy test (for females of childbearing potential), and urinalysis will be collected at Day -14 in order that results can be available at the latest on Day -7.
- Check for prior DMT compliance.
- Perform EDSS assessment.
- Perform SDMT and BVMT-R test.
- Recording of PedsQL/Ped NeuroQoL.
- Day -7 (phone call or visit): The Investigator will assess and confirm eligibility for alemtuzumab administration. If the patient is eligible for alemtuzumab administration, the prior DMT will be discontinued.

Premedication will be given to the patient and patient will be instructed to take premedication the day prior to the alemtuzumab administration in the morning and in the evening according to the schedule. Refer to [Section 8.2](#) for further details.

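### Section 9.3.2 promises about 1% of blood volume per visit, but its fixed 57 ml maximum does not meet that target in lighter children

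*Protocol*

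**What the plan says.** Protocol Section 9.3.2 sets two limits that depend on body size. Per visit, "sampling blood volume will be minimized to approximately 1% of total blood volume at each visit"; cumulatively, "approximately 3% of total blood volume over a 4 week period". It presents both as following international recommendations.

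The next paragraph gives planned volumes: "Blood sample volume will range from 9 to 57 ml, depending on tests required at study visits". It adds an average of 23 ml per visit and approximate totals of 350 ml in Year 1, 200 ml in Year 2 and 120 ml in each safety-monitoring year. It also allows further safety samples at the Investigator's discretion. It does not break the volumes down by visit, scale them to weight, or rank the percentages against the millilitres.

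Lighter patients are foreseen. Section 7.1 admits patients from age 10 with no minimum weight, and Section 4 states "The adult dose will be adjusted (reduced) proportionately for paediatric patients <50 kg".

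On spreading the draws:

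- Section 10.1.1 (Screening): "The above investigations may be performed on separate visits as long as all are completed within the 28 days prior to inclusion".
- Section 10.1.3: "Visit 3 assessments can be performed over multiple days".
- Sections 10.1.4 and 10.1.10: the M0 and M12 courses run over five and three infusion days. The PK samples are assigned to different days within each course (Sections 1.2.4 and 1.2.5).

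The Clinical Trial Summary lists the optional blood: "Immune Markers (optional): M0/D1 (baseline), M4, M12, M18 and M24/at EOTP".

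**The concern.** One paragraph makes a promise relative to the child's size, and the next gives a ceiling that ignores it. If the ceiling is larger than the promise for patients the protocol expects to treat, the statement of compliance is inaccurate for them. A site with a 35 kg child at the heaviest visit cannot tell from the text which figure to follow or which tube to leave out.

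What is at stake is patient protection and the accuracy of a stated figure.

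**Working it through.** **Inputs.** From Section 9.3.2: 1% per visit, 3% per 4 weeks, 9-57 ml per visit, average 23 ml, totals of 350, 200 and 120 ml per year. Assumption, not in the protocol: total blood volume of 70-80 ml/kg, with 65 ml/kg as a low sensitivity value.

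**The plan's own average.** Section 10.1 has 15 blood-draw visits in Year 1 (Visit 1, Visit 3 and Visits 4 to 16): 350/15 = 23.3 ml, which reproduces the stated 23 ml. It is a Year 1 average; Year 2 gives 200/12 = 16.7 ml and a safety-monitoring year 120/12 = 10 ml. The 57 ml cannot be rebuilt, because no volumes by visit or tube are given.

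**Without any assumption.** 57 ml is 1% of 5,700 ml. At 50 kg that needs 5,700/50 = 114 ml/kg; at 40 kg, 5,700/40 = 142.5 ml/kg.

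**With 70-80 ml/kg.** Share = 57/(weight × ml/kg).

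| Weight | 1% of volume | 57 ml as a share | 3% of volume | Left of 3% after 57 ml |
|---|---|---|---|---|
| 30 kg | 21-24 ml | 2.4-2.7% | 63-72 ml | 6-15 ml |
| 40 kg | 28-32 ml | 1.8-2.0% | 84-96 ml | 27-39 ml |
| 50 kg | 35-40 ml | 1.4-1.6% | 105-120 ml | 48-63 ml |
| 60 kg | 42-48 ml | 1.2-1.4% | 126-144 ml | 69-87 ml |
| 70 kg | 49-56 ml | 1.0-1.2% | 147-168 ml | 90-111 ml |

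57 ml equals 1% at 57/0.80 = 71 kg to 57/0.70 = 81 kg. At 65 ml/kg the share at 50 kg is 1.75%, so the conclusion does not depend on the value chosen. The 23 ml average meets 1% from 23/0.80 = 29 kg to 23/0.70 = 33 kg upward.

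**Where a 57 ml visit can fall.**

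1. A safety-monitoring year has 12 monthly draws (Table 3) totalling about 120 ml, each at least 9 ml. The annual visit is therefore at most about 120 − 11 × 9 = 21 ml, or 26 ml if 120 was rounded down from 125.
2. That annual visit takes hematology, full chemistry, thyroid tests, lymphocyte phenotyping and anti-drug antibodies. M24 takes the same, plus optional immune markers (Table 2). M18 has no antibody sample; M4 has neither antibody nor thyroid samples (Section 10.1.6).
3. If a given test uses the same tube volume throughout, non-optional blood at M4, M18 and M24 is about 21 ml or less. At 30 kg that is 21/2,400 = 0.9% to 21/2,100 = 1.0%, which meets the target.
4. The remaining 57 − 21 = 36 ml must come from something else. Screening adds hepatitis, HPV, TB and pregnancy tests. M0 and M12 add PK samples on more than one infusion day. M0, M4, M12, M18 and M24 add optional immune-marker blood.

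**Splitting.** Two draw days of 28.5 ml are 0.71-0.81% at 50 kg and 0.89-1.02% at 40 kg. At 30 kg, two draws are 1.19-1.36%, and three draws of 19 ml are 0.79-0.90%.

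**The case against.** The best reply is that the two sentences can be read together. The percentage is the undertaking and is softened by the word approximately; the 9-57 ml range describes what the tests need and is not a quota. Nothing instructs a site to exceed 1%. The average visit meets the target in nearly all plausible patients, and the heaviest blood is splittable, already multi-day or optional. Sample order could sit in the laboratory manual, which is not shown.

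Much of this stands and is why the point is minor. It does not remove the conflict: the protocol prints both figures, and approximately 1% can absorb the 1.0-1.4% at 60-70 kg but not the roughly doubled share at 40 kg.

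A reader might go further in three directions that the documents do not support.

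- **The four-week limit is breached.** One 57 ml draw stays within 3% even at 30 kg. Whether other draws in the same four weeks push the total over cannot be computed without volumes by visit.
- **M4, M12, M18 and M24 leave no room to split.** M12 spans three infusion days, with PK on Day 1 and Day 3, and Table 2 gives a ±7-day sampling window that covers M18 and M24. The Year 1 schedule table is not in the available text, so silence there cannot be assumed.
- **The cited international recommendation is violated.** That source is not available here. Only the protocol's own target can be tested.

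**Conclusion.** The point holds in a limited form. At the stated 57 ml maximum, the stated per-visit target of about 1% is not met in lighter children: mildly just under 50 kg (1.4-1.6% at 50 kg) and clearly at 40 kg and below (1.8-2.0% at 40 kg, 2.4-2.7% at 30 kg). The percentages rest on the assumed 70-80 ml/kg; the direction does not.

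The problem belongs to the heaviest visit or visits only. Those are Screening, the M0 or M12 course, or visits enlarged by optional immune-marker blood. This location rests on the approximate 120 ml yearly total and on constant tube volumes per test. The section does not say whether 57 ml includes the optional blood or adds up several infusion days; if it does, the draw on any one day is smaller. How many patients weigh less than 50 kg cannot be derived from the protocol.

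Severity is minor. This is an inconsistency about patient protection, with no effect on the primary endpoint, its analysis or power.

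**What to change.** Add to Section 9.3.2 that the limits of approximately 1% per visit and 3% per four weeks prevail over the 57 ml maximum. Express the first as a cap of about 0.7-0.8 ml/kg per draw day: 21-24 ml at 30 kg, 28-32 ml at 40 kg, 35-40 ml at 50 kg. When the cap is reached, safety samples are taken first, draws are spread over the days or window the visit already allows, and optional immune-marker blood is the first to be omitted.

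Dropping immune markers ahead of PK is sensible because "PK serum concentration and PK parameters" are a secondary endpoint. That order is a judgement, since Section 12.2 places PK blood under the same optional consent form.

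Alternatively, restate the paragraph to say that the largest visits exceed 1% in lighter patients.

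The cost is one or two sentences, and a matching sample order in the laboratory manual if it has none. The downside is some lost optional samples or an extra draw day in the lightest patients (two extra days at 30 kg if a full 57 ml were kept).

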9.3.3 ITP, cytopenia, and antiGBM surveillance and monitoring

In an effort to identify ITP early and minimize the risk of bleeding due to low platelet counts, this protocol requires safety measures including monthly blood testing to monitor CBCs with platelet count for monitoring for any cytopenia. Patients with certain abnormalities may be required to have more frequent blood tests. See [Appendix B](#) (Immune thrombocytopenia).

If a cytopenia is suspected, appropriate medical intervention should be promptly initiated, including referral to specialist.

Alemtuzumab has also been associated with antiGBM disease, which can cause a pulmonaryrenal syndrome known as Goodpasture's disease (21, 22). AntiGBM disease is a rare autoimmune disorder in which circulating antibodies are directed against an antigen normally present in the basement membranes of renal glomeruli and pulmonary alveoli. The target antigen is the alpha-3 chain of type IV collagen. The resultant clinical syndrome encompasses a spectrum ranging from mild or no renal involvement to rapidly progressive glomerulonephritis. Patients may develop pulmonary hemorrhage.

In an effort to identify potential cases of antiGBM disease early, all patients in the study will undergo monthly evaluation of serum creatinine levels alone or as part of a full chemistry panel and laboratory urinalysis (minimally including examination of protein and hemoglobin) with

microscopy. Follow up of abnormal results will be guided by the algorithm below in [Appendix B](#) (Anti-Glomerular Basement Membrane Disease).

